8.3. Screen Failures

Screen failures are defined as subjects who consent to participate in the study but are not subsequently enrolled. An enrolled subject is defined as one for which appropriate written informed consent has been obtained, who meets all eligibility criteria and is randomized to receive study drug. Subjects who fail to meet entry criteria may be eligible to rescreen at a later time.

8.4. Lifestyle Considerations

Subjects must refrain from consuming alcohol for the duration of the study.

CNS depressants in combination with lofexidine may increase the risk of hypotension and bradycardia. Subjects should be advised to be cautious prior to driving or operating heavy machinery if on concomitant CNS depressants during the study until they know how they react to study drug.

8.5. Subject Discontinuation Criteria

The Investigator or Sponsor may discontinue individual subjects from the study at any time if it is deemed clinically appropriate or for any reason, including the following:

- Cardiovascular events
 - QTcF >500 msec or >25% above screening value for both males and females.
 - New onset of clinically significant abnormal electrocardiogram (eg, second- or third-degree heart block or uncontrolled arrhythmia, prolonged QTcF interval).
 - Persistent signs or symptoms of hypotension, bradycardia, or hypoperfusion.

- Single occurrence of symptomatic bradycardia (as assessed by the Investigator, regardless of blood pressure) associated with chest pain, shortness of breath, or decreased level of consciousness.
- Medical intervention for cardiovascular event: Any medical intervention (nonmedication or medication inclusive) used for the treatment of any cardiovascular event, with the exception of a positional intervention in subjects displaying hypotension.
- Any other clinically significant cardiovascular signs or symptoms that would place the subject at risk.
- Evidence of repeated alcohol use (eg, 2 positive alcohol tests after Screening) during the study. Alcohol or other sedative/hypnotic withdrawal signs and symptoms developing following enrollment into the study.
- More than 2 repeat occurrences of opioid rescue medication usage reported by the subject after Screening.
- An intolerable AE or SAE; the relationship to study drug must be recorded in source.
- Requirement for a treatment that is prohibited (Section 9.4) by the protocol.
- Noncompliance with the protocol, including but not limited to showing evidence of illicit drug use while participating in the study or refusal or inability to continue opioid taper schedule per protocol.
- Lost to follow up: If a subject is lost to follow-up, repeated attempts (defined as a minimum of 3 telephone calls, followed by sending a letter) will be made to reach the subject. If repeated attempts are unsuccessful, lost to follow up will be recorded in the subject's source document and electronic case report form (eCRF) as the reason for early discontinuation.
- Withdrawal of consent: Subjects are free to withdraw from the study at any time, regardless of their reasons, and without prejudice to further treatment. In such cases, the subject will be asked about the reason(s) for the decision to withdraw consent and the reason(s) clearly documented in the subject's source document and eCRF. Subjects withdrawing consent will be asked to complete early discontinuation procedures but have the option to refuse.

8.6. Early Discontinuation Visit

If a subject is discontinued from the study before completion, regardless of whether they have received study drug, the reason for discontinuation must be documented in the subject's source document and eCRF. Whenever a subject is discontinued, the procedures/assessments listed for the EOS Visit in the Schedule of Assessments (Table 2 or Table 3) should be performed. If a subject discontinues on a scheduled visit, assessments completed at that visit should be entered into the eCRF for that scheduled visit. Assessments required for the EOS Visit that are not required at the scheduled visit (eg, a complete physical examination, clinical laboratory tests) should be completed and entered into the eCRF for the EOS Visit.

Subjects who prematurely discontinue the study will be instructed to taper study drug as described in Section 9.2.3 and to complete the at-home assessments for the study drug taper period (Table 4 or Table 5). Once discontinued, subjects may not re-enter the study.

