Enhanced treatment options for emerging opioid withdrawal symptoms during opioid taper regimens may permit development of more efficient tapering protocols, which in turn would have significant

impact on reducing risk to patients on chronic opioids and may positively impact health economic outcomes.

There is a notable lack of well-controlled data on the opioid withdrawal syndrome during an opioid taper in chronic non-cancer pain patients. Gradually tapering a patient's opioid dose with small reductions in dose over a prolonged period of time is a practice inherently designed to mitigate the potential for opioid withdrawal. LUCEMYRA's effectiveness in treating opioid withdrawal symptoms has been established in the setting of abrupt opioid discontinuation; however, has not been thoroughly evaluated in the setting of an opioid taper. Opioid tapers are often conducted over several weeks, if not months, resulting in the potential for at least cumulative use of LUCEMYRA for beyond 14 days. A clinical trial is necessary to assess for a signal of serious hypotension, bradycardia, syncope, hepatotoxicity, or rebound hypertension, or identify potential unexpected serious risks of long-term use of LUCEMYRA in the setting of an opioid taper as the majority of the existing safety data for LUCEMYRA is on less than 14 days of use. This pilot study is intended to inform critical study design elements for a future pivotal study to assess the safety and efficacy of LUCEMYRA for use beyond 14 days in the setting of an opioid taper.

Methodology:

This is a pilot, multicenter, randomized, double-blind, placebo-controlled, outpatient clinical trial to assess the safety and tolerability, and to estimate the effectiveness of LUCEMYRA for mitigating the symptoms of opioid withdrawal in the setting of an opioid taper in subjects with chronic non-cancer pain.

After a Screening period of up to 28 days, subjects will begin a planned 14-day complete taper of their pre-study opioid and will be randomly assigned (1:1) to either LUCEMYRA or matching placebo. Study drug will be administered through the opioid taper and for 5 days after the opioid taper is completed. Study drug will then be tapered over a 4-day period for a total of approximately 21 days exposure to study drug (Figure 1).

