8.6.1. Early Discontinuation Follow-up

If a subject discontinues from the study, the subject will be contacted 30 days after the last day of study drug administration, unless the subject withdraws consent and refuses post-study contact. This telephone contact will be recorded in the source document. If a subject discontinues participation due to an AE/SAE that is at least possibly related to study drug, the subject will be followed until the event has resolved, stabilized or otherwise explained.

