12.1.2. Vital Signs

Orthostatic vital signs will be measured in-clinic. Orthostatic vital signs will be measured first after the subject has been sitting for at least 5 minutes (systolic/diastolic blood pressure, pulse, and temperature) and then after the subject has been standing for at least 3 minutes (systolic/diastolic blood pressure and pulse). On Day 1, orthostatic vital signs should be assessed pre-dose and 1-hour post-dose of study drug. A post-dose assessment is not required after Day 1. When repeat vital signs are performed, temperature does not need to be collected (only systolic/diastolic blood pressure and pulse).

Resting vital signs (systolic/diastolic blood pressure and pulse) only will be measured at home using a vital sign monitor during phone calls after dose reductions, and every day during the 4-day study drug taper through the EOS Visit. Resting vital signs will be measured after the subject has been sitting quietly for at least 5 minutes and, during the study drug taper and after, will be taken twice daily, once in the morning and once in the evening.

Subjects should contact the Investigator if they experience signs or symptoms of hypotension, bradycardia, or orthostasis (eg, lightheadedness, slow heart rate, dizziness, feeling faint at rest or when standing up) or hypertension (eg, pounding headache, dizziness, palpitations). Subjects should contact the Investigator if they record an at-home vital signs measurement reaching or exceeding a systolic blood pressure of ≥ 180 mmHg, diastolic blood pressure ≥ 105 mmHg, or heart rate of ≥ 120 bpm. Symptomatic episodes of hypotension should be captured as an AE. Confirmed instances of meeting criteria for hypertension should be captured as AEs regardless of symptomology.

During phone calls, the Investigator should ask the subject for a vital sign measurement and review subject-measured at-home vital signs.

Blood pressure and pulse measurements taken in-clinic or at-home should be repeated after a 15-30 minute rest if they meet the following criteria:

- Hypertension: systolic blood pressure of ≥180 mmHg, diastolic blood pressure ≥105 mmHg, or heart rate of ≥120 bpm
- Hypotension: systolic blood pressure of ≤90 or a diastolic blood pressure of ≤60, and a heart rate <50 bpm

If the subject has a confirmed systolic blood pressure of ≥ 180 mmHg, diastolic blood pressure ≥ 105 mmHg, or heart rate of ≥ 120 bpm, and is symptomatic, the subject should be seen (preferably by the Investigator).

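### Section 8.6 does not clearly require blood pressure or heart rate readings in the week after the last dose for subjects who discontinue early, although rebound hypertension is a named safety signal

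*Combined protocol and SAP*

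**What the plan says.** The Rationale in Section 3.1 says a trial is needed to "assess for a signal of serious hypotension, bradycardia, syncope, hepatotoxicity, or rebound hypertension".

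**Subjects who follow the schedule.** Section 12.1.2 calls for home readings "every day during the 4-day study drug taper through the EOS Visit", taken morning and evening. Table 4 marks diary vital signs on Days 18-21 and again on Days 22-27, the second block under Safety Follow-up. Table 2 adds clinic vital signs at Visit 5 (Day 22) and EOS (Day 28). With an opioid taper pause, Tables 3 and 5 move all of this six days later.

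**Subjects who discontinue early.** Section 8.6 states: "Whenever a subject is discontinued, the procedures/assessments listed for the EOS Visit in the Schedule of Assessments" should be performed. It continues: "Subjects who prematurely discontinue the study will be instructed to taper study drug as described in Section 9.2.3", and they are to "complete the at-home assessments for the study drug taper period (Table 4 or Table 5". Section 8.6.1 adds that "the subject will be contacted 30 days after the last day of study drug administration". For that call, Table 4 footnote b lists the current opioid regimen, EQ-5D-5L and pain ratings. It does not list vital signs.

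**More general text.** Sections 3.1 and 7.1 have subjects come back to the clinic about a week after dosing ends, without limiting this to completers. Section 12.1.2 refers to twice-daily home readings both in the drug taper and afterwards, and asks for a measurement at phone calls. Table 2 footnote j, attached to the phone-call row, also includes a home vital signs review, but the Vital signs row has no mark at the 30-day call.

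**The concern.** The sponsor scheduled close monitoring of completers after drug is stopped, so its own design treats that week as informative. Section 8.6, the only section written for early discontinuers, stops home assessments when the drug taper ends.

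Section 12.1.2 makes a confirmed high reading an adverse event (AE) whether or not the subject has symptoms. That rule works only if a reading is taken. A silent rise that starts after the final dose could become an AE in a completer but would go unrecorded in a discontinuer handled strictly under Section 8.6.

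Section 8.5 lists cardiovascular events, intolerable AEs and inability to continue the opioid taper among the reasons for leaving, and these may differ between the arms. What is known about blood pressure in the first week off drug would then come mainly from a group defined by what happened after randomization.

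**Working it through.** **1. Day of last dose (reproducing the plan).** Section 9.3 sets the opioid dose to zero from Day 13, or Day 19 with a pause (Table 3 footnote o). Section 9.2.3 continues study drug for 5 days after the last opioid dose and then tapers it over 4 days.

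- Standard: last opioid dose Day 12; 12 + 5 = Day 17; drug taper Days 18-21; last dose Day 21.
- Pause: last opioid dose Day 18; 18 + 5 = Day 23; drug taper Days 24-27; last dose Day 27.

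This matches the 21 to 27 dosing days in Section 7.4 and the taper start days in footnote p of Tables 2 and 3. EOS falls 28 - 21 = 34 - 27 = 7 days after the last dose. The maximum duration of 28 + 27 + 30 = 85 days also matches Section 7.4.

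**2. When a discontinuer's EOS procedures happen.** Section 8.6 gives no interval from the last dose. It does say: "If a subject discontinues on a scheduled visit, assessments completed at that visit should be entered into the eCRF for that scheduled visit". Only the EOS items not already done are then added. That points to the day of discontinuation, before the drug taper, but does not say so outright.

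**3. Scheduled readings, at nominal visit days.**

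| | Completer | Early discontinuer, Section 8.6 as written |
|---|---|---|
| Drug taper, home | 4 x 2 = 8 | 4 x 2 = 8 |
| After last dose, home | 6 x 2 = 12 | 0 |
| After last dose, clinic | 2 (about 1 and 7 days off drug) | 0 if EOS procedures precede the drug taper |
| 30-day call | 0, or 1 if footnote j is applied | 0, or 1 if footnote j is applied |

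The six home days are Days 22-27, or Days 28-33 with a pause.

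**4. How much information could be lost (illustration only).** The documents give no discontinuation rate, so a range is assumed. Section 7.3 gives 30 subjects per arm. If a fraction d of an arm has no post-drug readings, n = 30(1 - d). With no events seen, the one-sided 95% upper bound on the event rate is 1 - 0.05^(1/n). At an assumed true rate of 5%, the chance of seeing at least one event is 1 - 0.95^n.

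| d (assumed) | n per arm | Upper bound, 0 events | Chance of at least 1 event |
|---|---|---|---|
| 0% | 30 | 9.5% | 78.5% |
| 10% | 27 | 10.5% | 75.0% |
| 30% | 21 | 13.3% | 65.9% |
| 50% | 15 | 18.1% | 53.7% |

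These figures show loss of precision only. They do not measure bias from selective dropout.

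**5. Pooling at EOS.** Section 13.4.2.1.4 summarises change from Baseline at each scheduled measurement. A subject who discontinues between scheduled visits has vital signs taken as part of the EOS procedures. If these are entered under EOS, that summary combines readings taken on drug with completers' readings about 7 days off drug.

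**The case against.** A reader might infer that early discontinuers have no reading at all after the last dose. The documents do not support that.

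- The timing of EOS procedures relative to the drug taper is not stated.
- The clinic return in Sections 3.1 and 7.1 is not restricted to completers, and the paragraph on premature discontinuation exempts nobody from it.
- Section 12.1.2 can be read as carrying home readings past the drug taper.
- Footnote j may add one reading at the 30-day call, though that is too late to say much about early rebound.
- A subject who stops without tapering would have EOS vital signs after the last dose.
- Section 12.1.7.1 provides follow-up for subjects taken off drug for liver tests. Sections 8.6.1 and 12.2.4 do so for those leaving because of an AE at least possibly related to study drug.

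A reader might also infer that rebound is measured almost only in completers, or that every discontinuer contributes nothing (6 to 15 of 30 per arm at an assumed 20% to 50%). That also goes too far. Compliant discontinuers supply 8 home readings while the dose steps down, and the contact and AE rules of Section 12.1.2 apply then. AEs are collected to 30 days after the last dose (Section 12.2.3). Any dropout count also includes people lost to follow-up or refusing contact, whom no amendment would measure.

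Finally, safety summaries are descriptive (Section 13.4.2), and criteria for notable vital signs are left to the SAP, so no formal rebound comparison is undermined.

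All of this narrows the point without removing it. The general sentences describe the ordinary visit sequence, while Section 8.6 is the specific rule for discontinuers. If their EOS procedures come before the drug taper, reading through EOS adds nothing. Symptom reports cannot detect silent elevation. At best, sites must choose between conflicting passages, and practice may vary.

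**Conclusion.** The point holds as a conflict between passages and a gap in what is expressly required. Under Section 8.6 as written, an early discontinuer has no clearly required blood pressure or heart rate reading in the week after the last dose, against 14 scheduled sets (12 home, 2 clinic) for a completer. The exposure is limited to asymptomatic elevation arising after the final dose. The zero rests on EOS procedures being done at discontinuation, before the drug taper, which is the likelier reading but not an explicit one.

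The number of subjects affected cannot be derived from the documents, and the precision figures depend on assumed dropout and event rates. The point is still worth acting on, because rebound hypertension is a stated safety question and the correction is cheap.

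**What to change.** Reconcile Sections 8.6 and 8.6.1, and the matching paragraphs in Sections 3.1 and 7.1, with Section 12.1.2 and Table 2 footnote j:

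- State that early discontinuers who agree to follow-up continue the existing twice-daily home vital signs diary after the drug taper for the same period as completers, to about 7 days after the last dose.
- State when the EOS procedures take place relative to the drug taper, and whether the 30-day call includes a vital signs reading.
- In the analysis, summarise post-drug vital signs by days since last dose, so that discontinuation readings taken on drug are not pooled with EOS readings taken about 7 days off drug.

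This changes data collection and tabulation only, not dosing. Subjects already have the monitor and the diary, so no added visit or call is needed. The cost is amendment wording, one more table layout and about one extra week of diary use. Compliance among subjects who have left will be incomplete, so the number with post-drug readings should be reported by arm.

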8.6.1. Early Discontinuation Follow-up

If a subject discontinues from the study, the subject will be contacted 30 days after the last day of study drug administration, unless the subject withdraws consent and refuses post-study contact. This telephone contact will be recorded in the source document. If a subject discontinues participation due to an AE/SAE that is at least possibly related to study drug, the subject will be followed until the event has resolved, stabilized or otherwise explained.

9. TREATMENT OF SUBJECTS

9.1. Randomization and Blinding

9.1.1. Randomization

Eligible subjects will be randomized in a 1:1 ratio to LUCEMYRA or placebo. The randomization will be stratified by total opioid dose, in MED, captured at Screening (<90 MED, \geq 90 MED). The subject's baseline opioid use and changes to doses for planned taper reductions should be submitted to and approved by the Medical Monitor prior to Day -1.

Subject randomization will be performed using a computer-generated randomization schedule, providing site staff with a randomization code linked to the study drug kit number to be used.

Hard copies of the study drug randomization schedule will be stored securely. Only medically necessary unblinding(s) will be allowed.

9.1.2. Maintaining and Breaking the Blind

All subjects, study personnel (including the Investigator, study coordinator(s), pharmacist/designee), and the Sponsor will be blinded to the identity of the study drug (active or placebo) administered to subjects.

An interim analysis will be conducted after approximately 30 subjects have completed or discontinued the study. For the interim analysis, the blind will be broken for the statistical programmers and Sponsor-designated reviewers. Unblinded results and individual subject treatment assignments will not be provided to subjects, Investigators, or other study personnel.

If an Investigator believes it is necessary to break the blind for reasons of subject safety, the Investigator must call the Sponsor's Medical Monitor (or designee) for consultation before unblinding. The decision to break the study blind should be made in cases of life-threatening emergency when knowledge of the treatment arm investigational agent will influence clinical management. If, after discussion with the Medical Monitor, it is determined that the study drug should be disclosed, medical personnel will be able to access this information via the randomization system. Circumstances surrounding unblinding of subjects must be documented in writing. Subject completion and withdrawal causality should be assessed by the Investigator before unblinding of treatment assignment but must not delay treatment in an emergency situation. The date and reason for the unblinding must be recorded in the subject's source record.

Contact information for the Sponsor's Medical Monitor is as follows:

9.2. Treatments Administered

9.2.1. Multimodal Pain Management Plan

Prior to randomization, the Investigator and subject should discuss and agree upon a multimodal pain management plan to be instituted during and after the opioid taper to help the subject

manage pain. A plan must be agreed upon and recorded prior to randomization; however, it can be updated throughout the study, as needed. Updates made to the plan should be recorded. Planned pharmacologic and non-pharmacologic treatments should be in compliance with Section 9.4.

9.2.2. Study Drug Preparation

No special preparation is required before dosing of study drug.

9.2.3. Study Drug Administration

Day 1 dosing with study drug will begin in the clinic as 1 tablet (LUCEMYRA 0.18 mg/tablet or matching placebo) QID for a total daily dose of LUCEMYRA 0.72 mg or matching placebo. Subjects will be instructed to take their study drug in the morning upon awakening and then every 5 to 6 hours thereafter. Doses should be taken 5 to 6 hours apart and no more than 4 times per day. At the Day 1 Visit (Visit 1), the Investigator should schedule a phone call with the subject, to occur prior to the second dose of study drug on Day 2, to review the subjects at-home vital signs measurement and how the subject is feeling. The subject will be instructed to contact the site if they experience signs or symptoms of hypotension, bradycardia, or orthostasis (eg, lightheadedness, slow heart rate, dizziness, feeling faint at rest or when standing up) while continuing to dose at home on Day 1. If the subject contacts the site on Day 1 reporting these symptoms, the Investigator should consider reducing the planned first daily dose on Day 2.

On Day 2 the subject will be instructed to take 2 tablets QID (LUCEMYRA 1.44 mg/day or matching placebo), unless Day 1 dosing was not well-tolerated. The subject should contact the site if they experience signs or symptoms of hypotension, bradycardia, or orthostasis (eg, lightheadedness, slow heart rate, dizziness, feeling faint at rest or when standing up) after the first daily dose. The Investigator will contact the subject on Day 2, prior to the second dose of the day, to review the subject's at-home vital signs measurement and how the subject is feeling. The Investigator should discuss with the subject any changes to dosing of study drug. Dosing instructions may include an increase to 3-tablets per dose due to subject report of intolerable opioid withdrawal symptoms, or a reduction back to 1 tablet per dose, due to intolerability of study drug.

On Day 3 and beyond, dosing will be at the discretion of the Investigator, as guided by subject tolerability of study drug and opioid withdrawal symptoms.

The dose of study drug may be increased to manage opioid withdrawal symptoms. If an increased dose of study drug is not well-tolerated, the dose can be decreased. A single dose of study drug should not exceed 4 tablets (LUCEMYRA 0.72 mg or matching placebo). The total daily dose of study drug should not exceed 4 tablets QID (LUCEMYRA 2.88 mg/day or matching placebo).

Dosing of study drug will continue for 5 days after the last opioid dose. Study drug will then be tapered over an additional 4 days. The following schedule will be followed over the study drug taper period:

- If taking 4 tablets QID (LUCEMYRA 2.88 mg/day or matching placebo) on fifth day after the last opioid dose
 - 3 tablets QID (LUCEMYRA 2.16 mg/day or matching placebo) for 1 day

- 2 tablets QID (LUCEMYRA 1.44 mg/day or matching placebo) for 2 days
- 1 tablet QID (LUCEMYRA 0.72 mg/day or matching placebo) for 1 day
- Study drug discontinued
- If taking 3 tablets QID (LUCEMYRA 2.16 mg/day or matching placebo) on fifth day after the last opioid dose
 - 2 tablets QID (LUCEMYRA 1.44 mg/day or matching placebo) for 2 days
 - 1 tablet QID (LUCEMYRA 0.72 mg/day or matching placebo) for 2 days
 - Study drug discontinued
- If taking 2 tablets QID (LUCEMYRA 1.44 mg/day or matching placebo) on fifth day after the last opioid dose
 - 1 tablet QID (LUCEMYRA 0.72 mg/day or matching placebo) for 2 days
 - 1 tablet twice daily (LUCEMYRA 0.36 mg/day or matching placebo) for 2 days
 - Study drug discontinued
- If taking 1 tablet QID (LUCEMYRA 0.72 mg/day or matching placebo) on the fifth day after the last opioid dose
 - 1 tablet twice daily (LUCEMYRA 0.36 mg/day or matching placebo) for 4 days
 - Study drug discontinued

